CT typically provides excellent anatomical detail with highly reliable image quality, and is thus amenable to quantitative techniques for detecting and characterizing the presence and the extent of low attenuation areas. Li et al. evaluated 565 lung cancer screening exams by computer-aided quantitative assessment of the percentage volume of the lung having low attenuation [42]. This study found that the amount of low attenuation lung tissue was an independent predictor for lung cancer risk, even after adjusting for smoking status and pack-years of smoking. Mets et al. developed a risk score calculated from the relative volume of low attenuation lung tissue under combined with other patient-specific clinical data such as BMI and smoking history to identify patients with clinically significant airflow restriction in a lung screening population [54], which has also been shown to predict important outcomes [48].

Imbio's quantitative lung analysis will automatically analyze a chest CT and quantify the percentage of lung volume with low attenuation. The algorithm, as a first step, automatically segments CT lung images into voxels corresponding to lung parenchyma and voxels corresponding to other tissues or background noise. A total volume of lung parenchyma is calculated for the patient. Low attenuation voxels are then identified based either on a dual-threshold technique or a classifier trained to identify radiologist-confirmed low attenuation areas of varying severity. Once low-attenuation voxels are identified, the total percent of lung with low attenuation can be calculated.

III. Study Aims

Primary study endpoints

- Calling a Quitline number.

Secondary study endpoints

- Smoking cessation as measured by salivary cotinine testing.

IV. APPROACH & STUDY DESIGN

Phase I Summary

In the earlier pilot project, Imbio designed a report that would increase a patient's motivation to make a quit attempt following a lung cancer screen by showing them the impact of smoking on their overall lung health (See complete Phase I final report in Appendix 1).

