Data management - Data will be stored in a secured, centrally located REDCap database. Investigators will oversee the REDCap database setup, data management, audit and edit plans to ensure data accuracy and completeness, and creation of the study's codebook with precise definitions and coding of all variables. A double-checking mechanism will be set up to ensure data completeness and accuracy. Strategies are set up for handling missing data, which are described below.

VI. Data Analysis, Sample Size and Statistics - [name], a biostatistician with the University of Minnesota School of Public Health, will analyze data from the RCT. Similar to standard methods for factorial designs in other therapeutic areas, analyses to address the primary aims will be a test of the main effect of the randomized interventions (i.e., report type and counseling type). All analyses will be by intention-to-treat, and include all participants randomized, regardless of whether they are lost to follow-up. The primary outcome measures will be a dichotomous comparison of 24-hour quit attempts (yes/no) at the time of the three-week follow-up, three-month follow-up, and six-month follow up and subject-reported readiness to quit based on the contemplation ladder among those who have not quit smoking. Secondary outcomes include cotinine-verified abstinence at three and six-months and use of smoking cessation services (dichotomous outcome) at 3 weeks, 3 and 6 months. Initially assessment will focus on the main effect of Report condition (Report vs. Usual Care) averaging or "pooling over" the Counseling condition on the continuous (readiness to quit) and dichotomous outcomes (24-hour quit attempt, abstinence, use of smoking cessation services) using a two sample t-test of the difference in the mean response and two-sided Wald-type test [60] of the difference in proportions, respectively, with a 0.05 significance level. Exact tests (e.g., Barnard's exact test) may be used if the number of successes (e.g., quit attempts, abstinence) is

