small. Separate analyses will be performed at each measurement time point (e.g., three-weeks, three-months, and six-months). A similar set of analysis can be performed to assess the main effect of the counseling condition. Logistic and linear models (for the dichotomous and continuous outcomes) with covariates for report condition, counseling condition, and their interaction will be used to assess if the Report and Counseling conditions significantly interact. If the interaction is significant, there will be an examination of whether there is a significant difference between the Report and Usual Care within each level of the Counseling condition. As an exploratory analysis to help guide future studies, a logistic regression model with quit attempt (yes/no) as the response will be utilized. Possible covariates include intervention group, gender, age, number of pack years, interest in quitting at baseline, risk perception at baseline, number of previous quit attempts, and findings from the CT scan, and their interaction with the Report condition. Similar models could be constructed for the other outcomes (abstinence, use of use of smoking cessation services). Additional linear regression models will be constructed for the other outcomes (readiness to quit). Additionally examination will be on whether or not changes in readiness to quit at 3 weeks mediate quit attempts, use of smoking cessation resources, and abstinence at 3 and 6 months using structural equation modeling.

Sample Size: The proposed RCT is powered for a main effects analysis of the Report (averaged over the Counseling condition) for the following outcomes a) at least one 24-hour quit attempt within 6 months of the CT scan b) accessing either formal cessation programs and/or FDA-approved medications within 6 months and c) readiness to quit as measures by the contemplation ladder.

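### Section III, the analysis text and the sample-size text name different primary endpoints, and no rule says which result decides the trial

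*Combined protocol and SAP*

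**What the plan says.** Three places in the current text describe what is primary.

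- **Section III, Study Aims.** The only primary endpoint is "Calling a Quitline number". No time window is given. Section IV (Usual Care) provides a dedicated telephone number so that calls can be captured, while Section V also collects quitline calls by self-report. Neither source is given priority.
- **Section VI, analysis text.** "The primary outcome measures will be a dichotomous comparison of 24-hour quit attempts (yes/no) at the time of the three-week follow-up", and again at three and six months, together with "subject-reported readiness to quit based on the contemplation ladder among those who have not quit smoking". Services are placed lower: "Secondary outcomes include cotinine-verified abstinence at three and six-months and use of smoking cessation services (dichotomous outcome") at the same three visits.
- **Section VI, Sample Size.** The trial is powered for "at least one 24-hour quit attempt within 6 months of the CT scan", for access to formal programs and/or medications within 6 months, and for readiness with no visit stated. These three are then called the primary hypotheses, and Table 2 gives their power.

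On testing, Section VI specifies a t-test for readiness and a "two-sided Wald-type test [60] of the difference in proportions, respectively, with a 0.05 significance level" for the dichotomous outcomes, and adds that "Separate analyses will be performed at each measurement time point". The analysis is to "include all participants randomized, regardless of whether they are lost to follow-up".

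**The concern.** A trial needs one statement of which result, at which time, shows that the intervention worked. Here the only endpoint that Section III calls primary is missing from the analysis and power text. Access to programs or medications is a primary hypothesis in the sample-size text, while use of services is secondary in the analysis text. Quit attempts and readiness are common to the two parts of Section VI, but quit attempts have three separate test dates in one part and a 6-month window in the other, and readiness has no deciding visit in either.

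The Project summary says the aim is to validate the Report clinically, and Section VII says the sponsor will then seek FDA approval or clearance. With the text as it stands, a positive finding on calls, on attempts at any visit, on readiness or on programs and medications could each be presented as the primary result. A null finding on one could be displaced by another. That cannot be repaired credibly once outcomes have been seen by arm.

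**Working it through.** **1. The three lists side by side**

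| Outcome | Section III | Section VI, analysis | Section VI, sample size | Table 2 power |
|---|---|---|---|---|
| Quitline calls | primary | not named separately | not named | none |
| 24-hour quit attempt | not listed | primary, three visits | primary, within 6 months | 98.7% / 89.2% |
| Readiness | not listed | primary, no deciding visit | primary, no visit | 99.9% / 93.2% |
| Services; programs/medications | not listed | services secondary | programs/medications primary | 92.4% / 81.2% |

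Section VI does say that assessment begins with the Report effect. That orders the two factors (Report, then counseling), not the endpoints or visits.

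**2. Reproducing Table 2**

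Inputs: N = 400 and the arm rates in Table 2, with equal allocation assumed, so 200 v 200 for the Report main effect. Averaging over counseling, row 1 gives (20+40)/2 = 30% v (40+60)/2 = 50%. Row 2 gives 27.5% v 42.5%.

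Unpooled Wald power = Φ(|p₁−p₂|/SE − 1.96), with SE = √[(p₁(1−p₁)+p₂(1−p₂))/200].

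- Row 1: SE = √(0.46/200) = 0.0480, power 98.65% (stated 98.7%).
- Row 2: SE = 0.0471, power 88.96% (stated 89.2%).
- Readiness (SD 2.9, difference 1.5 or 1.0): 99.9% and about 93% (stated 99.9% and 93.2%).
- Programs/medications (11.25% v 23.75%; 10% v 20%): 91.5% and 80.7%, or 92.3% and 81.5% when stratified by counseling (stated 92.4% and 81.2%).

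Table 2 is therefore sound for one unadjusted test per outcome.

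**3. False-positive chance if any one significant Report result counted**

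For k two-sided tests at 0.05 on jointly normal statistics, independence gives the upper limit, 1 − 0.95ᵏ. The documents give no correlations, so those below are assumed, with results from multivariate normal simulation.

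| Set of tests | k | Upper limit | Under assumed correlation |
|---|---|---|---|
| Analysis text: attempts and readiness, three visits each | 6 | 1−0.95⁶ = 26.5% | 22.5% to 10.8% |
| Same, readiness tested once | 4 | 18.5% | 16.4% to 9.3% |
| Three powered outcomes | 3 | 14.3% | 13.6% (r = 0.3), 10.9% (r = 0.7), 8.4% (r = 0.9) |

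The ranges for six and four tests run from (between-visit r 0.5, cross-outcome r 0.3) to a common r of 0.9.

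For quit attempts alone over three visits, the correlation can be derived if attempts are counted cumulatively: r = √[p₁(1−p₂)/(p₂(1−p₁))]. The 3-week rate is p₁ = (5+15)/2 = 10%, from the expected rates in Section VI. With a 6-month average of p₂ = 40% (Table 2 row 1, four arms), r = √(0.10×0.60/(0.40×0.90)) = 0.41. With p₂ = 27.5% (row 2, no-counseling arms), r = 0.54. With the 3-month rate assumed anywhere from 13% to 3 points below p₂, the chance is about 10–12%, against the 14.3% limit.

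**4. Power under the possible remedies**

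- One quit-attempt test within 6 months at 0.05: 98.7% or 89.2%, as in Table 2, with complete outcomes.
- The same with an assumed 20% missing: complete cases (160 per side) 96.2% or 81.3%. Counting missing as no attempt (24% v 40%; 22% v 34%) gives 93.6% or 76.9%.
- Three outcomes at 0.05/3 = 0.0167 each: quit attempts 96.2% or 78.5%; programs/medications 82.7% or 66.8%; readiness 99.7% or 85.1%.
- Quitline calls at 0.05 (pooled-variance test): with assumed usual-care call rates of 5%, 10%, 20% or 30%, 80% power needs about 13%, 20%, 32% or 43.5% with the Report.

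**The case against.** The Project summary states the aim as encouraging a quit attempt, and both parts of Section VI include quit attempts, so a reader might infer that this is the real primary outcome. That supports choosing it. It does not cancel the Section III heading or say whether the 3-week, 3-month or 6-month result decides.

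The document calls this a Phase II study, and it does not state that any one significant result counts as success. Strict family-wise control is therefore partly a matter of judgement, and the error rates in the working are conditional. This stands, but the contradiction about what is primary does not depend on a multiplicity argument.

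Section V says strategies for missing data are described later. None is visible in the text available, and Table 3, which is cited, is not visible either. The missing-data figures are therefore illustrations only. Table 3 is described as covering 6-month abstinence, so it would not supply power for Quitline calls.

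Finally, Section VI says the primary aims are tested by main effects of both report type and counseling type. The counts above cover the Report only, the factor for which the trial is powered. This point stands, and the amendment should also settle the status of the counseling test.

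**Conclusion.** The concern holds and should be corrected before outcomes are examined by arm. The sharpest conflicts are Quitline calls, primary only in Section III and without power, and services or programs and medications, secondary in one part of Section VI and primary in the other. No endpoint, visit, order or alpha split is decisive. The size is conditional on any one significant result being enough and, below the upper limits, on assumed correlations. The contradiction itself rests on the wording alone and needs no assumption.

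**What to change.** State either one primary endpoint at one time point for the Report main effect, tested once at two-sided 0.05, or several primary endpoints with a fixed testing order or alpha split. Use identical wording in Section III, the analysis text and the sample-size text, and say whether the counseling main effect is primary or secondary.

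The choice best supported by the documents, though not the only valid one, is at least one 24-hour quit attempt within 6 months. Its window must be reconciled: the sample-size text starts at the CT scan and Section V at consent attestation, up to about 3 days apart under the recruitment procedure. The handling of missing outcomes must be stated. If Quitline calls stay primary, give the source (captured or self-reported), window, assumed rates, power and test. If readiness stays primary, give its visit. Report the remaining outcomes and visits as secondary with confidence intervals.

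The cost is a text amendment to Sections III and VI, with no added participants or data. The drawback is that other endpoints lose primary status. Choosing quit attempts demotes the only endpoint in Section III and puts self-report ahead of captured calls. Keeping all three powered outcomes with an equal split avoids demoting any of them, but lowers power to as little as about 67% for programs and medications under the smaller effect.

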- Clinically significant health problems that make projected lifespan \leq 2-years
- LungRads Category 3 or 4 resulted out on screening CT

Recruitment and Consent - Randomized Controlled Trial participants will be recruited through the University of Michigan (200 participants) Health System and the HealthPartners Institute (200 participants).

- At HealthPartners, patients scheduled at HealthPartners Specialty Center will be given an informational flyer and consent form with return envelope during check-in for their Screening CT.
- Patients interested in participating in the study will be asked to contact the study coordinator by telephone within 72-hours (3-days) of their CT scan. During that call the coordinator will review the study requirements, read the consent form to the participant and attest to the patient's willingness to participate in the study. Participant will be asked to mail the last (signature) page of the consent to the coordinator in the envelope provided for back up hard copy.
- Consent forms will specifically request permission to share actual CT images with IMBIO in order to print a Patient Report based on the patient's own CT images. Specific permission will also be sought to share the Patient Report CT screening results with Mayo TTS and the Quitline representative.
- Following the screen, a radiologist will analyze the CT scan image and send the results to the patient's PCP. If the scan is read as a category 1 or 2 in the Lung CT Screening Reporting and Data System (Lung-RADS) [49], patients who have consented to study participation will be randomized to one of four treatment arms. If the scan is read as a category 3, 4A, 4B, or 4X in Lung-RADS the patient will be contacted by their primary care physician's office and told to schedule a follow up appointment. They will be sent a letter informing them they are not eligible for participation in the study after ordering physician has notified them of results and follow-up plans.

Randomization

Upon attestation of consent, eligible participants will be randomly assigned to one of four conditions using a central RedCap database:

1. Usual Care (w/ MN Quitline phone number);
2. Usual Care + Report (w/ IMBIO Quitline number);
3. Usual Care + Counseling; Or
4. Usual Care + Report (w/ IMBIO Quitline number) + Counseling incorporating results of report.

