Those patients randomized to receive the Report will have their radiology images loaded onto a secure flash drive by radiology staff. The images will be uploaded into a HIPAA-compliant web-based portal hosted by IMBIO for processing and generation of the Reports, which can then be downloaded and printed.

Randomization letters, usual care letters and/or reports (Groups 2 & 4) will be mailed to participants. (For participants randomized to Groups 1 & 3, generation and mailing of reports will be delayed until study participation has finished.)

Synopsis of Treatment Arms

Usual Care - Subjects participating in lung cancer screening through HealthPartners and the University of Michigan Health System are referred for screening from their primary care physician (PCP). HealthPartners and the University of Michigan Health System require PCPs to document in the medical order system that current smokers who require a lung cancer screen have been offered smoking cessation counseling prior to providing the screen, in accordance with CMS guidelines [50]. Once a patient is cleared for screening, they are able to schedule an appointment at an affiliated lung cancer-screening site. Following radiologist reading of the scans, eligible study patients randomized to the usual care group will receive a standard results letter in the mail notifying them of screening results with a phone number that will lead them to the state of MN Quitline. The phone number will differ from the MN Quitline number in order to capture calling data. The phone number will provide a short voice message to recipients and then transfer them to the MN or MI Quitline depending on their location.

Tobacco Dependence Counseling

Counseling will consist of one 45-minute session by telephone to occur within two weeks (preferably no more than 10-days) after the lung cancer screen. Counseling sessions will be in accordance with established cessation counseling protocols developed at the Mayo Clinic. Tobacco Treatment Specialists (TTS) will have a complete list of local resources and will facilitate participant enrollment and/or use of medications at the time of the call.

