Outcomes will be assessed at 3 weeks, 3 months, and 6 months. Timing of outcome follow up will begin at time of consent attestation. There will be assessment of participant self-reported use of resources including enrollment in face-to-face cessation programs, calls to quitlines, use of medications, and other smoking cessation services. Participants reporting abstinence at three and six month follow up will be asked to submit saliva cotinine samples to confirm self-reports.

A survey to assess readiness to quit, motivation to make a quit attempt, use of a smoking cessation quitline, quit attempts and long-term smoking abstinence will be developed by [name]. University of Minnesota Office of Measurements Services (Measurement Services) will administer follow up calls to assess readiness to quit, motivation to make a quit attempt, use of a smoking cessation quitline, quit attempts and long-term smoking abstinence. Measurement Services will be blinded to participant's conditions. All participants will receive follow up calls at 3 weeks, 3 months, and 6 months to assess calls to the quitline, readiness to quit, quit attempts, use of cessation aids (programs and medications), as well as current smoking following receipt of their lung cancer screen results.

Given the large number of subjects, Office of Measurement Services will input the survey into the Computer-Assisted Telephone Interviewing (CATI) Software[59] and train staff to ensure a consistent and effective approach.

[name] at the University of Minnesota will manage cotinine analysis. Participants reporting abstinence at 3 and 6 months will be asked to submit saliva samples by mail. A second consent form specific to cotinine collection will be mailed with the collection kit.

All participants will receive \$20 after each of the first and second follow-up calls, and \$70 after the final follow-up call. Participants who report abstinence will be provided an additional incentive of \$50 to provide a saliva sample for a cotinine analysis. A maximum of \$160 will be provided to participants as compensation for their time and as an incentive for their participation. Compensation will be provided as Target gift cards, mailed to patients address on record after confirmation of follow-up completion by University of MN Office of Measurement Services (OMS).

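### No survey is scheduled before randomisation, so change in readiness and the baseline attitude covariates in Section VI have no data source

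*Combined protocol and SAP*

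**What the plan says.** Section V (Data Collection Processes) gives the schedule: "Outcomes will be assessed at 3 weeks, 3 months, and 6 months". It adds that "Timing of outcome follow up will begin at time of consent attestation", but ties no measurement to that moment.

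Section IV (Recruitment and Consent) describes one study contact before assignment, a telephone call made by the interested patient: "During that call the coordinator will review the study requirements, read the consent form to the participant", after which the coordinator attests willingness. Section IV (Randomization) continues: "Upon attestation of consent, eligible participants will be randomly assigned to one of four conditions using a central RedCap database". Between the two, the documents describe only the Lung-RADS reading.

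Section VI (Data Analysis, Sample Size and Statistics) plans a structural equation model of whether "changes in readiness to quit at 3 weeks mediate quit attempts" and later outcomes. It also plans an exploratory logistic model whose possible covariates include "interest in quitting at baseline, risk perception at baseline, number of previous quit attempts", with interactions with the Report condition.

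On service use, Section VI powers the trial for access to formal programs or approved medication within 6 months, without requiring that the use be new. Section IV (Usual Care) says primary care must document that "current smokers who require a lung cancer screen have been offered smoking cessation counseling prior to providing the screen". No eligibility criterion concerns current use of a cessation aid.

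**The concern.** A change score needs a starting value. If the first contemplation-ladder score is taken at the 3-week call, after assignment, within-person change cannot be formed. Interest and risk perception asked at that point would no longer be baseline values, because the Report is designed to alter them.

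Substituting the 3-week level for the change would not answer the same question. Randomisation protects the path from Report to 3-week readiness. It does not protect the path from readiness to later quitting, where motivation that existed before entry is the obvious confounder. A baseline score is what allows that to be addressed, and it cannot be recovered once a participant has been assigned.

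The service-use outcome raises a related but lesser question. Everyone enters after a documented offer of counseling, so some may already be using a program or medication. Without a record of use at entry, continuing use cannot be separated from a new start.

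**Working it through.** **1. Does a pre-randomisation source exist?**

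- Section V lists three survey contacts, all after consent.
- The consent call has no questionnaire in its description.
- Payments are $20 + $20 + $70 for the three calls and $50 for saliva. The sum is $160, exactly the stated maximum, so no baseline interview is paid for.
- The Section VIII timeline has rows for the three follow-up calls and none for a baseline survey.

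Set against Section VI:

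| Variable | Source in the documents |
|---|---|
| Change in readiness | None before randomisation |
| Baseline interest, baseline risk perception | None |
| Previous quit attempts | None stated; could be asked later by recall |
| Age, pack-years | Eligibility items |
| CT findings | Screening scan |
| Gender | Presumably the medical record |

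**2. Do the primary tests or Table 2 need a baseline?** Inputs from Section VI: N = 400 (taken as 200 per side for the main effect; the allocation ratio is not stated), SD 2.9, two-sided 0.05.

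- Standard error = 2.9 × √(2/200) = 0.29.
- Power for 1.0 point = Φ(1.0/0.29 − 1.96) = 93.2%; Table 2 prints 93.2%.
- Power for 1.5 points = Φ(1.5/0.29 − 1.96) = 99.9%; Table 2 prints 99.9%.

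The table is reproduced from post-randomisation values alone.

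**3. What would a baseline ladder score add?** With assumed baseline correlation ρ, the adjusted SD is 2.9 × √(1 − ρ²). Power for 1.0 point, keeping 200 per side:

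- ρ = 0.3: SD 2.77, power 95.1%
- ρ = 0.5: SD 2.51, power 97.8%
- ρ = 0.7: SD 2.07, power 99.8%

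**4. Aid use at entry.** Pooling Table 2 over counseling gives (5% + 17.5%)/2 = 11.25% without the Report and (17.5% + 30%)/2 = 23.75% with it. The unpooled Wald standard error is √[(0.1125 × 0.8875 + 0.2375 × 0.7625)/200] = 0.0375, so power = Φ(0.125/0.0375 − 1.96), about 91.6%. Table 2 prints 92.4%; averaging the two within-counseling differences gives 92.3%.

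Now suppose Table 2's rates p mean new use, and a share b of every arm already uses an aid. If that use counts, each rate becomes b + (1 − b)p. If only new starts count, with all participants kept in the denominator, it becomes (1 − b)p. The difference is 12.5 × (1 − b) points either way; only the variance changes.

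| b (assumed) | Any use counts | Power | New starts only | Power |
|---|---|---|---|---|
| 5% | 15.7% vs 27.6% | 83% | 10.7% vs 22.6% | 90% |
| 10% | 20.1% vs 31.4% | 74% | 10.1% vs 21.4% | 88% |
| 15% | 24.6% vs 35.2% | 65% | 9.6% vs 20.2% | 86% |

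**5. False-positive rate.** With no Report effect and an 11.25% new-use rate in both groups, 400,000 simulated trials of 200 per group gave a rejection rate of 0.051 to 0.052 for b of 0, 10%, 20% and 30%. Carry-over use does not inflate it.

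**The case against.** The best defence is that absence is being inferred from silence. Section V schedules outcomes, and a baseline covariate is not an outcome. The account of the consent call also omits checking smoking status and pack-years, which must happen somewhere, so it is not exhaustive. The timeline has no rows for consent, randomisation or mailing of the Report either. The survey is still to be developed, the timeline refers to a questionnaire from another part of the project, and a codebook is to define every variable. A baseline module may therefore exist. This limits confidence, but it does not supply the missing step: the survey's stated use is the follow-up calls, and a site following this protocol would not collect the data.

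Four stronger readings are tempting and are not supported:

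- A reader might infer that the primary analyses fail. They compare post-randomisation values between randomised groups and need no baseline.
- A reader might infer that every baseline covariate is missing. Age, pack-years and CT findings are available, and the list is of possible covariates in an exploratory model.
- A reader might treat chance imbalance in starting readiness (95% range 1.96 × 0.29 = ±0.57 points, 38% of the 1.5-point target) as uncorrected error. It is already inside the t-test's standard error.
- A reader might infer that aids in use at entry are credited to the Report. They would count in all four arms, balanced in expectation, and so dilute the contrast. Section V also ties the call items to the period after participants receive their screening results. That narrows the window, though it does not clearly exclude continuing use.

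An offer of counseling is also not evidence of use. Table 2's 5% for Usual Care may already be total access, in which case use at entry could not exceed 5% and the printed power stands.

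**Conclusion.** The point holds as a mismatch between Sections V and VI. Change in readiness, baseline interest and baseline risk perception have no described pre-randomisation source, so the mediation-on-change analysis and the exploratory models using those covariates cannot be run as written. The primary between-arm tests and the readiness power in Table 2 are unaffected. The lost opportunity there is precision: 93.2% to about 97.8% power for a 1.0-point difference, at an assumed correlation of 0.5.

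The service-use limb is a definition gap, not a demonstrated miscount. Its avoidable cost is about 7, 14 or 21 points of power at 5%, 10% or 15% use at entry (90 − 83, 88 − 74, 86 − 65). This rests on an assumed prevalence and on Table 2 meaning new use; under the other reading its stated power is unaffected. The amendment should be made, with moderate confidence in the finding until the instrument and codebook can be checked.

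**What to change.** - On the consent call, before the REDCap assignment, record the contemplation ladder, the risk-perception items, the number of previous quit attempts and current use of cessation programs or medication. Add this baseline contact to Section V. If a baseline module already exists, cite it there with its timing.
- In Section VI, define change in readiness against that score, and adjust the readiness comparison for it.
- Define the service and medication outcome as a new start after randomisation, keep all randomised participants in the denominator, and say whether the Table 2 rates mean new or total use.

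The cost is a short amendment and a few minutes on a call that already takes place, including for some callers later excluded on their Lung-RADS result. The questions may themselves prompt some participants, but equally in all arms because they precede assignment.
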